7.4.3 Prescheduled or Elective Procedures or Routinely Scheduled Treatments

A prescheduled or elective procedure or a routinely scheduled treatment will not be considered an SAE, even if the patient is hospitalized; the Study Center must document all of the following:

- The prescheduled or elective procedure or routinely scheduled treatment was scheduled (or was on a waiting list to be scheduled) prior to obtaining the patient's consent to participate in the Study
- The condition that required the prescheduled or elective procedure or routinely scheduled treatment was present before and did not worsen or progress in the opinion of the Investigator between the patient's consent to participate in the Study and the timing of the procedure or treatment
- The prescheduled or elective procedure or routinely scheduled treatment is the sole reason for the intervention or hospital admission

7.4.4 Dosing Errors

Study Drug (ISIS 304801 or placebo) errors should be documented as Protocol Deviations. A brief description should be provided in the deviation, including whether the patient was symptomatic (list symptoms) or asymptomatic, and the event accidental or intentional. Dosing details should be captured on the Dosing Case Report Form. If the patient takes a dose of Study Drug (ISIS 304801 or placebo) that exceeds protocol specifications and the patient is symptomatic, then the symptom(s) should be documented as an AE and be reported per Section 7.2.

Should an overdose occur, the Investigator or designee should refer to the Guidance to Investigator's section of the Investigator's Brochure and contact Ionis within 24 hours.

7.5 Safety Monitoring Rules

In addition to the standard monitoring of clinical safety parameters, the following guidelines are provided for the monitoring of selected parameters chosen based on preclinical and clinical observations. For the purposes of safety monitoring baseline is defined as the average of Day 1 pre-dose assessment and the last measurement prior to Day 1.

Confirmation Guidance: At any time during the Study (Treatment or Post-Treatment Periods), the initial clinical laboratory results meeting the safety monitoring criteria presented below **must be confirmed** by performing measurements (ideally in the same laboratory that performed the initial measurement) on new specimens. All new specimen collections should take place as soon as possible (ideally within 3 days of the initial collection). For stopping rules, if the initial laboratory result is observed during the Treatment Period, the results from the retest **must be available** prior to administering the next dose of Study Drug (ISIS 304801 or placebo).

Re-dosing Guidance: Patients with initial laboratory test values that reach a stopping rule must not be re-dosed until the re-test results are available. In general, patients who do not meet the stopping rules based upon retest may continue dosing. However, the Investigator will decide whether additional close monitoring of the patient is appropriate. If any of the stopping criteria described below are met below and are confirmed, the patient will be permanently discontinued from further treatment with Study Drug (ISIS 304801 or placebo), evaluated fully as outlined below and will be entered into the post-treatment evaluation portion of the study. Consultation will be conducted between the Investigator and the Ionis Medical Advisor as needed.

7.5.1 Safety Monitoring Rules for Liver Chemistry Tests

The following rules are adapted from the draft guidance for industry, "Drug-Induced Liver Injury: Premarketing Clinical Evaluation," issued by the U.S. Department of Health and Human Services, Food and Drug Administration, July 2009. For a definition of baseline please refer to guidance above.

For patients with Baseline ALT or AST below 2 x ULN

In the event of an ALT or AST measurement that is >3 x ULN (or the greater of 2 x baseline value or 3 x ULN if the baseline value was $>ULN$) at any time during the Study (Treatment or Post-Treatment Period), the initial measurement(s) should be confirmed as described above. Additional, confirmatory measurements should also be performed if ALT or AST levels increase to 5 x ULN.

For patients with baseline ALT or AST between ≥ 2 and < 3 x ULN

In the event of an ALT or AST measurement that is 2 x the baseline level any time during the study (Treatment or Post-Treatment Period), the initial measurement(s) should be confirmed as described above. Similarly, confirmatory measurements should also be performed if ALT or AST levels increase to 5 x ULN.

Frequency of Repeat Measurements: Patients with confirmed ALT or AST levels that are continuing to rise should have their liver chemistry tests (ALT, AST, ALP, INR and total bilirubin) retested at least bi-monthly until levels stabilize and begin to recover (ALT and AST levels become ≤ 1.2 x ULN or 1.2 x baseline value).

Further Investigation into Liver Chemistry Elevations: For patients with confirmed ALT or AST levels > 3 x ULN [or the greater of 2 x baseline value or 3 x ULN if the baseline value was $> \text{ULN}$], the following evaluations should be performed:

1. Obtain a more detailed history of symptoms and prior and concurrent diseases
2. Obtain further history for concomitant drug use (including nonprescription medications, herbal and dietary supplement preparations), alcohol use, recreational drug use, and special diets
3. Obtain a history for exposure to environmental chemical agents and travel
4. Serology for viral hepatitis (HAV IgM, HBsAg, HCV antibody, CMV IgM, and EBV antibody panel)
5. Serology for autoimmune hepatitis (e.g., antinuclear antibody (ANA))

Additional liver evaluations, including gastroenterology/hepatology consultations, hepatic computed tomography (CT) or MRI scans, may be performed at the discretion of the Investigator, with consultation with the Sponsor Medical Monitor as needed. Repetition of the above evaluations should be considered if a patient's ALT and/or AST levels reach 5 x ULN.

7.5.2 Safety Monitoring Rules for Renal Function

Patients with confirmed persistent changes that are observed over 2 consecutive visits, at least 7 days apart, for the criterion below should be retested every two weeks with serum creatinine and urine chemistries until creatinine and P/C ratio stabilize:

- P/C ratio change from baseline $> 50\%$ and ≥ 1.5 ULN

7.5.3 Safety Monitoring Rules for Platelet Count Results

Actions to be taken in the event of reduced platelet count are shown in Table 3 in Section 7.6.3.

7.5.4 Safety Monitoring for Minor Bleeding Events

Minor bleeding events are those that do not fulfill the criteria for major bleeding or clinically relevant, non-major bleeding events (which are defined in Section 7.6.3), for example excess bruising, petechiae, gingival bleeding on brushing teeth. If a minor bleeding event occurs, additional testing of coagulation parameters (aPTT, PT, INR) and platelet count should be performed, and the Investigator will consult with the Sponsor Medical Monitor as needed.

7.5.5 Safety Monitoring for Constitutional Symptoms

Patients will be instructed to promptly report any signs of symptoms of fever or constitutional symptoms that may arise during the study and the Investigator should closely evaluate all potential causes, including

concomitant illness. If patients experience persistent constitutional symptoms, the Investigator will determine whether additional monitoring or laboratory tests are required, with consultation with the Sponsor Medical Monitor as needed.

7.5.6 Safety Monitoring for LDL-C Elevations

Beginning at Week 16 (after which treatment is unblinded), laboratory alerts will be in place to notify the Investigator if a patient has an LDL-C > 160 mg/dL on two consecutive visits. If this occurs, the Investigator will consider initiation or adjustment of treatment to lower LDL-C according to published guidelines (e.g., initiate statin therapy, increase the statin dose for patients who are already on treatment, add ezetimibe if on maximal statin therapy)⁵².

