1.2 Secondary/Tertiary Objectives

To evaluate the efficacy of 16 weeks of ISIS 304801 as compared to placebo (between group comparison) on additional lipid, glycemic, hepatic, and cardiovascular parameters (see Outcome Measures), as well as safety and tolerability of ISIS 304801. In addition, the effects of ISIS 304801 (defined as tertiary outcomes) as compared to immediately prior to treatment (pre-post within subject comparison) for 16 weeks on these outcomes will be evaluated.

2. Introduction

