4.1 Design/Randomization

This study has two components. Initially, subjects will receive ISIS 304801 or placebo, in a 1:1 randomized, double-blinded fashion for 16 weeks. Randomization will occur after verification that all eligibility criteria have been met. The randomization will be stratified by use of lipid-lowering medications. After completion of 16 weeks, all subjects will receive ISIS 304801 for 12 months in an open-label extension (OLE) phase. After discontinuation of ISIS 304801 (due to study end or any other reason) subjects will be followed for an additional 12 week withdrawal phase when possible. Patients who experience benefit (triglyceride lowering $\geq 50\%$) may receive an additional 12 months of open label drug (up to 24 months, total). This period may initiate immediately following the standard 12 month OLE, or following the withdrawal phase.

- 1° outcome (Δ in log₁₀ triglycerides):
 - C vs D
 - F vs G
- 2°/3° outcomes – within subject comparisons:
 - C vs E
 - F vs H
- Placebo vs drug comparisons
 - C vs H

1

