4.2 Outcome Measures

4.2.1 Primary outcome:

Efficacy of 16 weeks of ISIS 304801 as compared to placebo (between group comparison) on the change in log₁₀ fasting triglycerides (TG).

4.2.2 Secondary outcomes:

Efficacy of 16 weeks of ISIS 304801 as compared to placebo (between group comparison) on:

Lipids

- Percent change in fasting TG
- Absolute change in fasting TG
- Change in lipolysis rate measured using stable isotope tracers
- Change from baseline in liver volume and hepatic steatosis (as assessed by magnetic resonance imaging [MRI] and magnetic resonance spectroscopy [MRS])
- Lipoprotein lipase activity

Glycemic

- Change in total body insulin sensitivity using the hyperinsulinemic euglycemic clamp
- Change in hepatic glucose production and hepatic insulin sensitivity using stable isotope tracers in combination with the hyperinsulinemic euglycemic clamp
- Change in hemoglobin A1c (HbA1c)
- Change in fasting plasma glucose

Safety

- Safety and tolerability of ISIS 304801
- Prospectively adjudicated acute pancreatitis events (Atlanta classification) and Major Adverse Cardiovascular Events (MACE)

Pharmacokinetic

- Plasma ISIS 304801 level

4.2.3 Tertiary/Exploratory outcomes:

Efficacy of 16 weeks and 16 months of ISIS 304801 as compared to immediately prior to treatment (pre-post within subject comparison) on:

Lipids

- Change in other fasting lipid measurements: high-density lipoprotein cholesterol (HDL-C), low-density lipoprotein cholesterol (LDL-C), total cholesterol (TChol), very low-density lipoprotein cholesterol VLDL-C, non-HDL-C, apolipoprotein B (apoB), apolipoprotein B-48 (apoB48), apolipoprotein A1 (apoA1), apolipoprotein CIII (apoC-III; total, chylomicron, VLDL, LDL and HDL), and free fatty acids
- Change in lipoprotein particle size/number by nuclear magnetic resonance (NMR)
- Triglyceride (and other lipid particle) clearance following mixed meal testing

Glycemic

- Change in 24-h glucose (using 7-point plasma blood glucose)
- Change in fasting and area under the curve for insulin and C-peptide during mixed meal testing
- Reduction in insulin use

Adipose tissue

- Change in skinfold thickness and dual-energy X-ray absorptiometry (DEXA)
- Change in abdominal VAT and SAT volumes
- Change in adiponectin and leptin
- Change in body weight and waist circumference

Cardiovascular

- Carotid intima-media thickness (by ultrasound)
- Coronary artery wall thickness and diameter change after hand-grip exercise (by MRI)

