5.1 Sample Size Justification

The primary outcome variable is the change in log₁₀ fasting triglycerides from before treatment to 16 weeks of active drug treatment compared to placebo groups.

Preliminary data are available for 28 patients treated with ISIS 304801 and 24 treated with placebo. For the ISIS 304801 group, these data show a difference from baseline to follow-up of -423 (SD 400, 95% CI -578 to -268) mg/dL and -0.485 (SD 0.221, 95% CI -0.57 to -0.40) log₁₀ mg/dL. Converting the difference in log₁₀ mg/dL to a percent change [$100 \times (10^{-0.485} - 1)$] results in a percent change of -67% (95% CI -73% to -60%). For the placebo group, the absolute change is -12 (SD 406, 95% CI -12 to 184) mg/dL and -0.011 (SD 0.224, 95% CI -0.105 to 0.084) log₁₀ mg/dL. The percent change for the placebo group is -3% (95% CI -21% to 21%).

For comparison of placebo and ISIS 304801 we have chosen a SD of 0.25 log₁₀ mg/dL and a difference of 0.50 log₁₀ mg/dL. A trial with 5 patients in each group has 79% power to detect a difference of 0.50 log₁₀ mg/dL triglycerides in the change from baseline to follow-up between the ISIS and placebo groups, assuming a SD of 0.25 log₁₀ mg/dL and a two-sided significance level of 0.05.

Where preliminary data were available, sample size calculations were performed for secondary and tertiary study outcomes in addition to the primary outcome. The preliminary data and power estimates for a sample size of 10 subjects (using one-sample t-test for off versus on drug comparisons) are summarized in the table below. Based on these calculations, the study should be adequately powered to detect differences in total body insulin sensitivity, hepatic insulin sensitivity, fasting glucose, apoC-III serum level, HDL-C, VLDL-C, and apolipoprotein B48.

Based on these calculations, we plan to enroll a maximum of 20 patients, with a goal of 10 patients completing the study (defined as completing 16 weeks of active drug treatment). The accrual ceiling of 20 is planned because subjects will consent to the study prior to screening, thus we are accounting for up to 10 screen failures in the accrual ceiling.

	Outcome	Model	Treatment	Treat- ment Duration	Mean of Δ on-off drug (SD)	Power
Primary outcome	Absolute change log[serum triglycerides] (mg/dL)	High TG +/- diabetes and/or fibrate	ApoCIII ASO 300 mg/wk	16 wk	-0.48 (0.22)	>0.95
	% change serum triglycerides (%)	High TG +/- diabetes and/or fibrate	ApoCIII ASO 300 mg/wk	16 wk	-63 (20)	>0.95

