5.2 Statistical Methods for Data Analysis

Descriptive statistics such as mean and standard deviation (or median and interquartile range) will be used to summarize data in raw scale or change from baseline per visit.

The primary outcome, change in log₁₀ TG at Week 16 from baseline, and continuous secondary outcomes will be compared between ISIS 304801 and placebo groups using either two-sample t-test or Wilcoxon rank sum test as appropriate based on change from Baseline at Week 16. Changes from baseline based on tertiary/exploratory outcomes as well as change on log₁₀ TG at Week 16 will be examined using either one-sample t-test or Wilcoxon signed rank test as appropriate.

Repeated measures analysis of covariance using linear mixed models will be conducted in order to investigate trends on selected response variables and to compare active and placebo group while possible covariates are taken into account. There are three possible covariates: (1) Baseline level of the outcome of interest, (2) Baseline level of ApoCIII, and (3) Change in ApoCIII before and after the 16 week active drug intervention.

Inclusion of covariates will be checked using linear mixed models by checking Akaike Information Criteria (AIC) with inclusion of one covariate at a time

Analyses will include all available data even if patients do not adhere to their assigned treatments. Additional analyses will examine the effect of adherence to study results. We will also investigate the effect of missing data on the results using standard methods for missing data.

A p-value of 0.05 or less is considered significant.

6. Experimental Plan

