6.4.5 Safety Assessments

1. Liver function, Kidney function, Platelets, LDL, and coagulation tests (detailed in Appendix B): Monitoring of the above (except for platelets) will be performed every 4 weeks for the first 6 months of treatment, and every 8 weeks thereafter, per the Study Schedule (Appendix A). Platelets will be monitored every week for the duration of the study.
2. Self-monitoring of blood glucose: In subjects with diabetes, a home glucometer will be distributed to patients who do not have one already at the first inpatient visit for home-based glucose monitoring (“Self-Monitored Plasma Glucose” or SMPG). Training on the use of the glucometer will be provided as needed. Fasting SMPG will be self-measured in the fasting state: daily if the patient is on insulin therapy, and weekly if on oral antidiabetic therapy.
3. Urinalysis: Urinalysis and urine protein to creatinine ratio will be conducted as per the Study Schedule (Appendix A).
4. Echocardiogram: Echocardiography for assessment of left and right ventricular function and mitral and aortic valve function will be conducted per the Study Schedule (Appendix A). Cardiologists reviewing echocardiograms at NIH will not be aware of treatment assignment during the randomized period. Results will be provided to the DSMB for their review.

5. **EKG:** Standard 12-lead EKGs will be performed after the patient has been resting in a supine position for at least 5 minutes per the Study Schedule (Appendix A).
6. **Troponin T:** Cardiac troponin T will be measured per the Study Schedule (Appendix A).
7. **Pregnancy test:** Pregnancy tests will be performed on female patients with reproductive potential at each inpatient visit.
8. **Pancreatitis:** All patients will be given an instruction card that must be presented to the treating physician if a suspected case of pancreatitis occurs. The card will explain that the patient is in a clinical trial and that serum lipase and/or amylase measures should be done in order to adjudicate the event, based on Atlanta Classification⁵¹. If serum or amylase activity is less than 3 x ULN, imaging, preferably contrast-enhanced computed tomography (CT), should be considered to confirm the diagnosis of acute pancreatitis per the Atlanta Criteria.

7. Human Subject Protection

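### LDL-lowering therapy added from Week 16 under 7.5.6 would make the Week 32 (placebo-first) and Week 68 LDL-C changes a drug-plus-therapy effect, and 5.2 plans no supplementary analysis

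*Combined protocol and SAP*

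**What the plan says.** - **Trigger and action (7.5.6).** Alerts run from Week 16. LDL-C above 160 mg/dL on two consecutive visits is the trigger, and then "the Investigator will consider initiation or adjustment of treatment to lower LDL-C according to published guidelines". The examples given are starting a statin, raising its dose, or adding ezetimibe.
- **Outcome (4.2.3).** LDL-C, non-HDL-C, total cholesterol and apoB are tertiary. They are analysed within subject under the label "Efficacy of 16 weeks and 16 months of ISIS 304801 as compared to immediately prior to treatment". No control group enters that comparison.
- **Data rule (5.2).** "Analyses will include all available data even if patients do not adhere to their assigned treatments". The tertiary test is a one-sample t-test or signed rank test on change. The mixed models list three possible covariates: baseline outcome, baseline apoC-III and change in apoC-III. Concomitant medication is not among them. The adherence and missing-data sentences do not cover a value that was observed but altered by a new statin.
- **What already helps.** Section 5.2 will "summarize data in raw scale or change from baseline per visit", so on-drug values before any added therapy will be visible. Concomitant medication is reviewed at the contacts in 6.3.6 and Appendix A.
- **Timing.** LDL is among the tests in 6.4.5, where "Monitoring of the above (except for platelets) will be performed every 4 weeks for the first 6 months of treatment". The Precis places the 16-week on-drug assessment of placebo-first patients after four months of open-label drug, which is Week 32. Under 4.1, "all subjects will receive ISIS 304801 for 12 months in an open-label extension (OLE) phase", so Week 68 is about 16 months of drug for drug-first patients and 12 for placebo-first.
- **A parallel case.** For hyperglycemia rescue, 7.5.8 asks for efficacy assessments before rescue if possible and lets affected tests be cancelled. Section 7.5.6 has no counterpart.

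**The concern.** The preliminary data in 5.1, from patients with high triglycerides but not lipodystrophy, predict that LDL-C will rise on the drug by 31.3 mg/dL. That is an unfavorable change, and the plan expects it enough to write a monitoring rule for it. The rule acts on the patients with the highest on-drug values and, if followed, lowers exactly those values before the endpoint is read. With no concurrent control after Week 16 and all values retained, the pre-post change then combines the drug's effect with that of the added therapy. The expected LDL-C rise would look smaller, and the expected falls in non-HDL-C, total cholesterol and apoB would look larger, than the drug alone would produce. At stake is how a tertiary lipid safety signal is described, not whether the drug lowers triglycerides.

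**Working it through.** **1. The plan's own figure.** Section 5.1 gives an LDL-C change of +31.3 (SD 47.3) and power 0.46 for 10 subjects, one-sample t-test. The noncentral t distribution with df 9, noncentrality 31.3/47.3 × √10 and two-sided alpha 0.05 gives 0.464, which reproduces it. The other three also reproduce: non-HDL-C 0.419 (stated 0.42), total cholesterol 0.242 (0.24), apoB 0.085 (0.09). None of the four is among the outcomes 5.1 calls adequately powered, whose list ends "fasting glucose, apoC-III serum level, HDL-C, VLDL-C, and apolipoprotein B48".

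**2. Which results can be reached.**
- Drug-first 16-week value: read at Week 16, when alerts only begin. Not reached.
- Primary and secondary comparisons with placebo, and the 1.2 objective "as compared to placebo (between group comparison) on additional lipid, glycemic, hepatic, and cardiovascular parameters": all end at Week 16. Not reached.
- Placebo-first 16-week on-drug value (Week 32): visits at Weeks 20 and 24 are on drug and can supply two consecutive values above 160. Reached.
- Week 68, both sequences: reached.

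**3. Simple arithmetic.** Suppose one treated patient would have been at 160 mg/dL, and therapy lowers LDL-C by 20-40% (assumed). The loss is 32-64 mg/dL. The mean change falls by 32/5 = 6.4 to 64/5 = 12.8 mg/dL among five placebo-first patients, or by 3.2 to 6.4 among ten.

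**4. Simulation at Week 32.** From 5.1: observed change mean 31.3, total SD 47.3. Assumed, because the documents do not give them: baseline mean 100 (SD 20), visit-to-visit SD 15 or 20, change independent of baseline, stable on-drug level, therapy effect 20, 30 or 40%. Trigger: both the Week 20 and the Week 24 value above 160. At least one million patients per setting.

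| | Visit SD 15 | Visit SD 20 |
|---|---|---|
| Proportion triggering | 0.221 | 0.192 |
| All data, full uptake (20/30/40% effect) | 22.8 / 18.6 / 14.3 | 24.1 / 20.5 / 16.8 |
| Treated patients dropped, full uptake | 17.2 | 20.7 |
| Last pre-therapy value used, full uptake | 32.0 | 32.5 |

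The true value is 31.3. At half uptake the all-data result is 22.8 to 27.7. With five planned placebo-first patients, 0.19-0.22 × 5 is about one patient.

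**5. Pooled 16-week contrast.** With equal sequences, only the placebo-first half shifts. Full uptake: (31.3 − 24.1)/2 = 3.6 to (31.3 − 14.3)/2 = 8.5. Half uptake: (31.3 − 27.7)/2 = 1.8 to (31.3 − 22.8)/2 = 4.2. The standard error is 47.3/√10 = 15.0 for ten patients and 47.3/√5 = 21.2 for five. The pooled shift is at most about 0.6 of a standard error, and the placebo-first shift of 7.2 to 17.0 is also below its own.

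**6. Week 68.** With alerts at eight visits from Week 20 to Week 64, the same model has 32-33% triggering. The all-data result is +8 to +20 at full uptake and +20 to +26 at half. Using the last pre-therapy value gives 33.1 to 34.7. This relies more heavily on the stable-level assumption, over a much longer interval.

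**The case against.** **The plan never says it wants the drug effect without added therapy.** Keeping all data is a legitimate treatment-policy choice, and the resulting change correctly describes drug plus guideline care. This stands, so the all-data analysis should not be called wrong. But 4.2.3 names the effect of ISIS 304801, no estimand is stated, and a reader will take the number as the drug's effect.

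**The effect is conditional and small against noise.** This also stands. The investigator need only consider treatment; if nobody is treated there is no distortion. The outcomes are tertiary with stated power of 0.46 or less.

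**The size rests on assumptions.** True. A reader might infer that the rise could almost vanish by taking a baseline mean of 120 (SD 20). That puts about 31% of patients above 130 mg/dL, whereas exclusion 8b bars LDL-C above 130 on maximal tolerated statin therapy. Truncating baseline at 130 gives about +9 to +22 even with that mean. A negative correlation between baseline and change would also shrink the distortion somewhat.

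**Existing summaries may suffice.** Per-visit changes, medication review and possibly a mixed model for LDL-C would reveal the problem. They would not give an alternative Week 32 or Week 68 result.

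**Section 6.2.1 seems to forbid the added therapy.** A reader might see a contradiction, since 6.2.1 excepts only insulin and sulfonylureas from its stable-dose rule. The specific safety rule in 7.5.6 governs, so this is a drafting matter.

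**Conclusion.** The point holds as a minor one, conditional on at least one triggered patient receiving added therapy. Then the Week 32 result in placebo-first patients and the Week 68 result in both sequences answer a drug-plus-therapy question and understate the LDL-C rise due to the drug. The direction and the gap in 5.2 follow from the text. The size does not: under the stated assumptions a true +31 reads about +14 to +24 at Week 32 in placebo-first patients at full uptake, or +23 to +28 at half uptake. For the other three lipids only the direction is claimed.

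It would be wrong to infer that the trial's efficacy conclusions are compromised. Every primary and secondary comparison, and the 16-week value of drug-first patients, is complete before the rule can act.

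**What to change.** In 5.2:

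- Keep the all-data pre-post analysis and say that it estimates drug plus any added therapy.
- Add one supplementary LDL-C analysis in which each treated patient's endpoint is the last on-drug value before added LDL-lowering therapy. Make it the main supplement at Week 32, and only a labelled sensitivity analysis at Week 68. Extend it to non-HDL-C, total cholesterol and apoB where interim values exist.
- Do not drop treated patients. That removes the largest rises and reads +17 to +21 in the two-visit model at full uptake.
- Report the number treated by sequence and time point.
- Report Week 68 separately by sequence, as 16 and 12 months of drug.

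Optionally, except treatment under 7.5.6 from the stable-dose rule in 6.2.1 for consistency.

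The cost is one paragraph. LDL-C needs no new samples. For the other three lipids, 6.4.5 names only LDL among the interim lipid tests, and the copy of Appendix A read here shows no laboratory rows, so interim values could not be confirmed.

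The downside is that the substituted value comes from an earlier time on drug, as early as Week 24 (8 weeks on drug) for placebo-first patients. It is also selected slightly upward, by about 1-2 mg/dL in the group mean at Week 32 and 2-3 at Week 68, if the on-drug level is stable. Putting so early a value into a Week 68 result is why it should serve there only as a sensitivity analysis.
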